**Figure 9–1 Process flow for inhibitor testing**

### 9.3.3.6 FVIII recovery

Blood samples collected for FVIII recovery in this study are samples taken as part of the routine treatment monitoring schedule established by the Physician.

In accordance with the EMA guideline, the Physician is encouraged to test for FVIII recovery at 0, 10-15, 50-75 and ~100 EDs as outlined in [Table 9–2](#). Time and date of collection and result should be recorded in the pCRF. Novo Nordisk also offers to provide analysis of FVIII recovery samples i.e. 30 min post-dose, at a Central Laboratory selected by Novo Nordisk. No recovery samples are expected for patients on on-demand regimen.

### **9.3.3.7 FVIII trough level assessment – Local lab**

#### **Trough level (FVIII)**

The Physician can at his/her discretion perform trough level assessments at any visit. The trough level is defined as the lowest level of FVIII measured immediately prior to dosing and reported as (IU/mL). The trough level will be determined at the local laboratory.

### **9.3.3.8 HIV status and T cell subset: CD4+– Local lab**

- HIV status (includes HIV antibody and viral load, if HIV antibody positive)
- T cell subset: CD4+, if the patient is HIV positive the last value of CD4+ T cells (no more than 6 months prior to study entry) should be recorded

### **9.3.3.9 Central Laboratory tests**

If the Physician is performing blood sampling for FVIII inhibitor and/or FVIII recovery test according to local clinical practice, the Physician is encouraged to send these samples to the Central Laboratory for analysis. Central Laboratory data will be reported to Novo Nordisk electronically in a manner that anonymity of patients will be maintained and, to the Physicians by fax or e-mail. Upon review of the laboratory results the Physician should sign and date the laboratory reports. The Central Laboratory is requested only to report analyses dictated by this protocol.

The quality control of the Central Laboratory test results will be performed according to the regulations and specifications set by the authorities at the location of the Central Laboratory used for this study.

Laboratory kits for blood sampling of analyses to be performed by the Central Laboratory will be provided to the sites.

Blood samples analysed by the Central Laboratory for measurement of inhibitors towards FVIII will be performed according to the Nijmegen modification of the Bethesda assay.

Blood samples for FVIII recovery will be analysed by the following two different assays:

#### **One-stage clot activity assay**

The one-stage bioassay (FVIII:C assay, clot assay) measures the activity of the compound in a specific process (clot formation). The FVIII:C assay is a modified one-stage clotting assay.

#### **Chromogenic activity assay**

A bioassay (FVIII:C chromogenic assay), which measures the activity of the compound with a two-stage method.

Recovery sampling should be performed in a non-bleeding state, and is assessed by the two methods specified above. If dose administered is known, incremental recovery is calculated as [IU/mL]/[IU/kg].

In case a patient receives treatment with his current FVIII product at Visit 1, and a recovery test is performed, the incremental recovery result is reported.

### **9.3.4 Other assessments**

#### **9.3.4.1 Demography**

Collected as allowed by local law.

- Date of birth
- Ethnicity
- Race

#### **9.3.4.2 Body measurement**

- Body weight, wearing light clothing only and without shoes (kg/lbs)
- Height, without shoes (cm/inches)

#### **9.3.4.3 FVIII genotype**

All patients/parents/legally authorised representative (LAR) will be asked if available result(s) of previous FVIII genotype test(s) at Visit 1 may be documented in the study. If a genotype test is performed during the study, the result will be documented, if consented to, by the patients/parents/LAR. The Physician, patient or parent(s)/LAR have the right to refuse to provide such documentation. This will not stop the patient from participating or to continue in the study.

#### **9.3.4.4 Haemophilia treatment history**

- Prophylaxis/preventive regimen within the last 50 ED or the last two years
  - Number of months on prophylaxis
  - Current dose and frequency of dosing
  - Recombinant or plasma FVIII product
  - Number of doses with turoctocog alfa
  - Average number of bleeds per month
  - Documentation covering the last 50 ED/two years
- On-demand regimen within the last 50 ED or the last two years
  - Number of months with on-demand regimen
  - Recombinant or plasma FVIII product
  - Number of doses with turoctocog alfa
  - Average number of bleeds per month
  - Documentation covering the last 50 ED/two years

- History of switching FVIII products (type of products (from/to)), if available
- Surgeries within the last five years
  - Date of surgery
  - Indication
  - Recombinant or plasma FVIII product
  - Duration of surgical treatment
- Number of vaccinations in the last 12 months

#### **9.3.4.5 Concomitant illness and Medical history**

A concomitant illness is any illness that is present at the start of the study i.e. at the first visit. Details of all concomitant illnesses and medical history must be recorded at study entry i.e. at visit 1. The information collected for concomitant illness and medical history should include diagnosis, date of onset, date of resolution or continuation. A clinically significant worsening of a concomitant illness must be reported as an AR, see section [11.3](#) if the worsening is related to turoctocog alfa. If the change influences the patient's eligibility to continue in the study, the monitor must be informed.

Details on medical history will be recorded at the Baseline visit during a medical interview and review of relevant medical records. In the event that a diagnosis is unknown, the description of symptoms should be recorded.

#### **9.3.4.6 Concomitant medication**

A concomitant medication is any medication, other than the study product which is taken during the study. Details of any concomitant medication should be recorded at study entry i.e. at the first visit. Any changes in concomitant medication should be recorded at each visit as they occur. The recommended information collected for each concomitant medication includes trade name or generic name, indication, start date and stop date or continuation. If a change is due to an AR then this should be recorded and reported according to section [11.3](#). If the change influences the patient's eligibility to continue in the study then the monitor should be informed.

#### **9.3.4.7 Haemophilia details**

- Diagnosis of haemophilia A (date)
- Classification of haemophilia A and FVIII level (%) from medical history
- Underlying gene defect (if known)
- Clinical suspicion of inhibitors, including transient inhibitors, from medical history
- Result of inhibitor tests and/or FVIII recovery values (including dose given and weight of the patient, for the last 5 years if available)

#### **9.3.4.8 Family history of haemophilia**

History of relatives with haemophilia A (as recalled by patient or parent/LAR or Physician)

### **9.3.4.9 Diary**

Diaries will be used in this study. The patient should be asked to bring the diary(ies) to every visit to the site.

The following data should be captured by the patient and/or parent:

- Treatment
  - FVIII product used
  - Prophylaxis treatment
  - Every single dose level and strength
  - Date and time of dose administration
- Bleeds
  - Date and time of onset of bleeding episode
  - Treatment of bleeding episode
  - Location of the bleed (specify location e.g. joint, muscular etc.)
  - Type of bleed (spontaneous, traumatic)
  - Haemostatic drug used for treatment
  - Every single dose level(s), strength(s) and time(s) of administration
  - Other therapy used (compression, ice or other)
  - Date and time of stop of bleeding episode
  - Severity of the bleed (Mild/Moderate or Severe)
  - Clinical evaluation of the haemostatic response (Excellent, Good, Moderate or None)

The Physician should carefully instruct the patient in how to evaluate a bleed, the haemostatic response after treatment and how to complete the diary. The Physician is recommended to retrain the patient, if needed.

Entries made in the diary should preferably be reviewed by the Physician together with the patient/caregiver at each visit to the clinic; and should be entered in the pCRF by the site staff. The information in the patient's diary is regarded as source data. If information missing in the diary is available in the medical records, this information can be used.

In case study product administration is performed at the site, this should be entered in the medical record and subsequently in the pCRF for the respective assessment visit, by the Physician. The study product must not be reported in the diary when the administration is performed at the site.

### **9.3.5 Study product**

The study product is the commercially available turoctocog alfa product manufactured by Novo Nordisk in vials containing lyophilised powder with rFVIII (human coagulation factor VIII

(recombinant)/INN name: turoctocog alfa)), and with solvent in a prefilled syringe. The powder is to be reconstituted with the solvent for injection in accordance with the Instruction For Use of the product.

Study product is to be administered according to approved product information (US PI, EU SmPC or corresponding local prescription information).

Commercially available turoctocog alfa used in this study should be stored according to the relevant Product Information for the products (US PI, European SmPC or corresponding local prescribing information).

The study product (i.e. the commercially available turoctocog alfa) will not be sponsored by Novo Nordisk.

### **9.3.5.1 Packaging and labelling of study product**

These must be as available in the market by prescription and purchase/supply as in routine practice and according to local regulations.

### **9.3.5.2 Auxiliary supply**

All items needed for reconstitution and administration of the study product will be supplied with the commercially available turoctocog alfa product.

## **9.4 Data sources**

It is the intention of this non-interventional study to observe routine treatment of the individual patient. Data and results available in patient's medical record from assessments and laboratory sampling performed according to clinical practice at the participating sites will be recorded in the pCRF as described in section [9.3](#). Treatment and information related to bleeding episodes will be captured in a patient diary by the patient or parent/caregiver as described in section [9.3.4.9](#). In case a patient is unable to enter a treatment or bleeding episode in the diary, or is hospitalised, it should be reported in the patients record and subsequently in the pCRF by the Physician.

For information on potential confounding variables please refer to section [9.9](#).

## **9.5 Study size**

Sample size is based on regulatory (EMA) requirements. According to the present version of the EMA guideline for factor VIII products data from at least 200 patients with 100 EDs are required. At least 30% of these patients should be <12 years of age, corresponding to 60 patients.

Several of the patients in the guardianTM2 (NN7008-3568) trial have already accomplished 100 EDs. As of 28-Aug-2012 167 patients in the guardianTM2 (NN7008-3568) trial has more than 100 EDs. Of these 53 are children. Based on this, the sample size for the present study will be a total of

approximately 50 patients of which at least 10 patients (20%) should be <12 years old at time of enrolment.

## **9.6 Data management**

### **9.6.1 Data management**

Data management is the responsibility of Data Management, Novo Nordisk Headquarters. Data management may be delegated under an agreement of transfer of responsibilities to another data management unit within Novo Nordisk or to a CRO.

The patient and the biological material obtained from the patient will be identified by a patient number, study site, and study ID number.

Appropriate measures such as encryption or deletion must be enforced to protect the identity of human subjects in all presentations and publications as required by local/regional/national requirements. Appropriate measures such as encryption of data files will be used to assure confidentiality of patient data when it is transmitted over open networks.

Laboratory data will be transferred electronically from the Central Laboratory performing clinical analyses. The electronic laboratory data will be considered source data. In cases where laboratory data is transferred via non-secure electronic networks, data will be encrypted during transfer.

### **9.6.2 Case Report Forms and rules for completing**

Novo Nordisk will provide pCRFs for data capture in this study. Print legibly using a ballpoint pen. Ensure that all questions are answered and that no empty data blocks exist. Ensure that no information is recorded outside the data blocks.

If a test/assessment has not been done and will not be available, indicate this by writing “ND” (not done) in the respective answer field in the pCRF. If the question is irrelevant (e.g. is not applicable) indicate this by writing “NA” (not applicable) in the respective answer field. Further guidance can be obtained from the instruction in the CRF. By signing the affirmation statement, the Physician confirms that the information is complete and correct.

#### **9.6.2.1 Corrections to CRFs**

Corrections to the data on the pCRFs must only be made by drawing a straight line through the incorrect data and by writing the correct value next to data that has been crossed out. Each correction must contain initials, date and explanation (if necessary) by the Physician or the Physician’s authorised staff. If corrections are made by the Physician’s authorised staff after the date of the Physician’s signature on the affirmation statement, the statement must be signed and dated again by the Physician. Corrections necessary after the pCRFs have been removed from the Physician’s site must be documented on a Data Clarification Form (DCF). Such corrections must be approved by the physician or her/his authorised staff.

### **9.6.2.2 CRF flow**

The Physician must ensure that data is recorded on the pCRFs as soon as possible after data is available (preferably within 3 days). pCRFs are produced on No Carbon Required paper with one original and one copy page. The top page (original page) is transferred by the monitor to the unit responsible for data entry as specified by Data Management, Novo Nordisk. The copy page is to be archived at site with the Physicians study documentation. Laboratory reports should preferably be signed and dated by the Physician on the day of the review of the analysis results and be retained at the study site. The results from the local laboratory should be entered on the pCRF for each patient. Central Laboratory results will be transferred electronically to Novo Nordisk and loaded into the study database by Novo Nordisk. Laboratory reports from the Central Laboratory will be provided to the Physician.

When the final non-interventional study report is available the data will be archived by Novo Nordisk in Oracle Clinical version 4.6.4 or a later version.

## **9.7 Data analysis**

Novo Nordisk will be responsible for the statistical analyses.

All summaries will show results for the full group of patients and for the subgroups of patients with endogenous FVIII level <1% and 1-2% at inclusion, as well as for the subgroups of patients below and above 12 years of age.

### **9.7.1 Statistical methods**

No formal testing of statistical hypotheses will be performed. Evaluation of data will be based upon descriptive statistics, i.e. summary tables, listings, and figures. Categorical data will be summarised by frequency tables while continuous data will be summarised by mean, standard deviation, minimum and maximum value.

### **9.7.2 Interim analysis**

An interim analysis covering all endpoints is planned to be performed with a data-cut 18 months and 35 months after the first patient data entry.

### **9.7.3 Primary endpoint**

The incidence rate of inhibitors ( $\geq 0.6$  BU for central laboratory analyses, or above the specific local laboratory reference range) represented as the percentage of patients developing inhibitors will be calculated and a 1-sided 97.5% upper confidence limit will be provided based on an exact calculation for a binomial distribution. For the calculation of the incidence rate the numerator will include all patients with inhibitors confirmed by laboratory except those patients who have received a positive inhibitor test result after inclusion in the study for a test performed prior to first dose of turoctocog alfa. The denominator will include all patients in the trial exposed to turoctocog alfa,

except those patients who have received a positive inhibitor test result after inclusion in the study for a test performed prior to first dose of turoctocog alfa, these patients will be listed separately.

In addition, the time to inhibitor development will be presented by Kaplan Meier plot. Furthermore, an annualised rate of inhibitors per patient year will be calculated using a Poisson model allowing for over-dispersion with a log-link function and the logarithm of the time spent in the trial as offset, if appropriate.

Analyses and presentations will be made for each treatment regimen (preventive treatment or on-demand treatment) and for all patients, and furthermore for each patient subgroup (Severity of Haemophilia A: severe, moderately severe or patients with surgery/invasive procedure).

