### 8.2 Endpoint(s)

#### 8.2.1 Primary endpoint

- Incidence rate of FVIII inhibitors ( $\geq 0.6$  BU for central laboratory analyses, or above the specific local laboratory reference range) represented as the percentage of patients developing inhibitors.

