### **9.3.3.5 FVIII inhibitor testing**

Blood sampling for inhibitor detection can be performed according to local clinical practice. As described in the EMA guideline, the Physician is encouraged to test for FVIII inhibitors according to [Table 9-2](#), preferably at least 48 hours after last treatment. If the patient is already being treated with turoctocog alfa at inclusion, the result of the inhibitor sample taken prior to initiated treatment

with turoctocog alfa must be available and negative. After inclusion in the study Novo Nordisk offer to provide analysis for FVIII inhibitors at a Central Laboratory selected by Novo Nordisk.

A positive inhibitor test is defined as  $\geq 0.6$  BU for central laboratory analyses, or above the specific local laboratory reference range. A patient has a confirmed inhibitor if the patient has been tested positive for inhibitors at two consecutive tests preferably within two weeks.

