**Table 9–2 Recommended laboratory scheme for FVIII inhibitors and recovery**

	0 EDs	10-15 EDs	50-75 EDs	~100 EDs
FVIII inhibitors	X 	X 	X 	X 
FVIII recovery	X	X	X	X

A 48 hours washout period is recommended

[figure not shown]
In the event that a patient has a positive inhibitor test obtained within 4 weeks prior to first dose of turoctocog alfa, the patient cannot be included in the study according to inclusion criteria no. 5, see section [9.2.2](#). In the event that a patient has a positive inhibitor test result after inclusion in the study for a test performed prior to first dose of turoctocog alfa, the patient may proceed in the study but will not be included in the full analysis set. In the event that a patient has a positive inhibitor test ( $\geq 0.6$  BU for central laboratory analyses, or above the specific local laboratory reference range) after inclusion and dosing in the study, the patient should visit the clinic again according to local practice (recommended to be performed as soon as possible - preferably within 2 weeks) to take a confirmatory inhibitor test on a separately drawn sample. The confirmatory sample should preferably be taken prior to any change of treatment. Even if the second inhibitor test is positive, the patient may continue in this study.

If this is decided, dosing, dosing frequency and more frequent visits for inhibitor sampling, if applicable, will be decided by the Physician based on the clinical evaluation. If a patient is to be withdrawn due to a confirmed inhibitor test, the Physician is encouraged to schedule an End of study visit (Visit 3) according to local clinical practice, and preferably within 1 month.

A positive inhibitor test should be reported as an AESI, see section [11.3](#). If the presence of inhibitors is confirmed by a second test this should be reported as a serious adverse reaction (SAR), see section [11.3](#). If the second inhibitor test is negative this should be reported as a follow-up to the reported AESI, see section [11.4](#). When lack of therapeutic effect is indicated by bleeding or laboratory findings, the Physician is encouraged to sample for FVIII inhibitor detection.

It is recommended that the Physician should upon a clinical suspicion of inhibitor development perform a FVIII inhibitor test.

The recommended process of inhibitor testing in case of a positive inhibitor test during the study is outlined in [Figure 9–1](#).

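### The primary endpoint is worded by the positive-test threshold but the analysis counts only confirmed inhibitors, so a positive that is never repeated is scored as no event

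*Protocol*

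**What the plan says.** **Endpoint.** Protocol section 8.2.1 defines the primary endpoint as an incidence rate of FVIII inhibitors, "represented as the percentage of patients developing inhibitors". Its only qualifier is the assay threshold: at least 0.6 "BU for central laboratory analyses, or above the specific local laboratory reference range". The primary objective (8.1.1) and the abstract carry the same qualifier. None of them mentions confirmation.

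**Definitions.** Section 9.3.3.5 has two. "A positive inhibitor test is defined as" is followed by that same threshold. The next sentence reads: "A patient has a confirmed inhibitor if the patient has been tested positive for inhibitors at two consecutive tests preferably within two weeks".

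**Analysis.** Section 9.7.3 repeats the threshold and then states that "the numerator will include all patients with inhibitors confirmed by laboratory". For the rest of the fraction, "The denominator will include all patients in the trial exposed to turoctocog alfa". The only patients taken out of either part are those with a positive result on a sample drawn before the first dose.

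**Repeat test.** After a post-dose positive, section 9.3.3.5 (text below Table 9–2) says "the patient should visit the clinic again according to local practice" for a separately drawn confirmatory sample, recommended as soon as possible and preferably within 2 weeks. Section 11.2 also uses should and preferably. Section 9.3.1 rules out extra visits on account of the study.

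**The concern.** The event is described in one place by a threshold that a single test can meet, and counted in another by a rule that most naturally needs two. The two rules differ for any patient with a post-dose positive and no second test. Section 9.7.3 keeps that patient in the denominator and out of the numerator, exactly like a patient who tested negative throughout, and no other section says otherwise.

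Such a patient is plausible under this design. The last recommended inhibitor sample (Table 9–2) is at about 100 exposure days, which is also when Visit 3 ends participation (Table 9–1, section 9.3.1.3). A positive at that point has no later study visit at which it could be confirmed. Early leavers are the other group: starting regular treatment with another FVIII product requires withdrawal (9.2.4), and patients still on study at close-out may be contacted by phone only (9.3.1.3).

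Immunogenicity is the primary objective of this safety study. A rule that can only leave events out pushes the reported rate down, and events are expected to be very few.

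**Working it through.** **1. The protocol's own figures.** The protocol has no power or precision calculation to reproduce. Section 9.5 takes the sample size from a regulatory count: 200 − 167 = 33 patients and 60 − 53 = 7 children still needed, against a planned 50 and 10. Section 9.7.1 plans no hypothesis test. The figure at stake is the percentage in 9.7.3 with its exact one-sided 97.5% upper limit.

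**2. Where each kind of patient falls under 9.7.3, taking confirmed as defined in 9.3.3.5.**

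| Post-dose result | Denominator | Numerator |
|---|---|---|
| All tests negative | in | out |
| Positive, repeat negative | in | out |
| Positive, never repeated | in | out |
| Two consecutive positives | in | in |

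The third row is unresolved but is treated like the first.

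**3. Size.** Inputs: n = 50, 70 and 80, the approximate numbers completing, included and screened at baseline in section 9.2.1. The number of unresolved positives is not in the protocol; I assume 1 or 2, with no confirmed inhibitor.

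For x events in n patients, the limit U solves P(X ≤ x | n, U) = 0.025, so U is the 0.975 quantile of a Beta(x + 1, n − x) distribution. For x = 0 this reduces to U = 1 − 0.025^(1/n). At n = 50, for example, 1 − 0.025^(0.02) = 7.11%.

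| n | As planned, x = 0 | One unresolved positive counted | Two counted |
|---|---|---|---|
| 50 | 0% (7.11%) | 2.00% (10.65%) | 4.00% (13.71%) |
| 70 | 0% (5.13%) | 1.43% (7.70%) | 2.86% (9.94%) |
| 80 | 0% (4.51%) | 1.25% (6.77%) | 2.50% (8.74%) |

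Cells show the percentage and, in brackets, the upper limit. As a check, P(X ≤ 1) at the x = 1 limit is 0.025 for each n.

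**4. Against the expected number of events.** Section 7.2 gives about 3 inhibitors per 1000 patient-years in previously treated patients. With 70 patients and an assumed 1 to 2 years each, 70 × 1 × 0.003 = 0.21 and 70 × 2 × 0.003 = 0.42 events are expected. One unresolved positive would exceed the expected total.

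**The case against.** Several objections have force.

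- **The two passages can be read together.** A reader might infer that the endpoint counts a single positive test. Section 8.2.1 does not say so; it gives a threshold and is silent on how many tests make a case. The threshold could define a positive test and confirmation could define a case. That is a sensible reading, but 8.2.1 does not state it.
- **The phrase in 9.7.3 is not tied to the two-test rule.** It could mean any inhibitor detected by a laboratory, in which case an unrepeated positive would count. Since 9.3.3.5 defines a confirmed inhibitor, the two-test reading is the natural one. If both stay open, the numerator is not fixed.
- **The repeat is not optional.** A reader might call it that, but the protocol says it should be done. Recommended, not mandatory, is accurate.
- **A later test can confirm.** Two weeks is only a preference, and sampling is also recommended at 10–15, 50–75 and about 100 exposure days and on lack of effect. This stands: a positive is unresolved only if no further test is ever done, which narrows the exposure mainly to the sample near 100 exposure days and to early leavers.
- **The positive is not hidden.** It is reportable within 24 hours as an adverse event of special interest and followed up (11.2 to 11.4). This stands; the loss is confined to the primary estimate.
- **Confirmed-only is defensible.** The earlier programme is described in terms of confirmed inhibitors (7.2), and a single assay positive may be false. This stands, and it argues against making a mixed definition the sole primary numerator.
- **The handling rule could sit in the statistical analysis plan.** It could, but the mismatch between endpoint and numerator is within the protocol.

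**Conclusion.** The point holds in a limited form. The endpoint wording and the counting rule do not match, and under the natural reading of 9.7.3 a post-dose positive that is never repeated is scored as inhibitor-free. The direction is downward. One such patient would raise the percentage by 1.25 to 2.0 points and the upper limit by about 2.3 points (n = 80: 6.77 − 4.51 = 2.26) to 3.5 points (n = 50: 10.65 − 7.11 = 3.54) if counted.

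This rests on two assumptions: that confirmed in 9.7.3 carries the meaning given in 9.3.3.5, and that at least one unresolved positive occurs with no confirmed inhibitor. The protocol gives no number for the latter.

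A reader might also infer that unresolved positives will be lost selectively, because a positive result prompts a product change. That is plausible but no section shows it, and patients with a confirmed inhibitor may stay in the study. Nor does one patient's classification overturn a formal conclusion, since the analysis is descriptive with no threshold or comparator. It does materially change the one figure the study is meant to deliver.

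**What to change.** - In 8.2.1 and 9.7.3, state one case definition and refer in both to the two-test definition in 9.3.3.5.
- In 9.7.3, state that a post-first-dose positive without a negative repeat is not scored as inhibitor-free, and show these patients as a separate unresolved category.
- Beside the confirmed percentage, report with the same exact limit (a) the percentage that counts unresolved positives as events and (b) the percentage with any post-first-dose positive.
- List separately the patients whose positive was followed by a negative repeat.

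The cost is a few sentences in two sections and two further percentages in the report. The added figures may include false positives that were never repeated and so look slightly less favourable; showing them beside the confirmed percentage lets the reader judge. The change concerns counting and reporting only, with no change to retesting practice or patient care.
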